3.9 Study Enrollment

Patients may be enrolled on the study once all eligibility requirements for the study have been met. Patients who give informed consent for the protocol in order to undergo screening for eligibility are not considered enrolled and should not be enrolled until the screening is completed and they are determined to meet all eligibility criteria. Study enrollment is accomplished by going to the Enrollment application in the eRDES system. (<https://cogmembers.org/apps/erdes>) If you have problems with enrollment, refer to online help in the Applications area of the COG website. Patients must be enrolled before treatment begins with the exception of Day 1 intrathecal chemotherapy, which can be administered at the time of the diagnostic LP. The date protocol therapy is projected to start must be no later than five (5) calendar days after the date of study enrollment. Patients must not receive any protocol therapy prior to enrollment.

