4.2.2 Concomitant Medications

4.2.2.1 Corticosteroids: Prednisone or methylprednisolone for ≤ 120 hours (5 days) may be administered for cytoreduction up to 24 hours prior to the start of protocol therapy and as treatment for allergic reactions or for physiologic replacement/stress dosing of hydrocortisone for documented adrenal insufficiency. Corticosteroids are not allowed for other indications. If used to modify **immune adverse events** related to prior therapy, ≥ 14 days must have elapsed since last dose of corticosteroid (See [Section 4.1.6.1.d](#)).

4.2.2.2 Investigational Drugs: Patients who are currently receiving another investigational drug.

4.2.2.3 Anti-cancer Agents: Patients who are currently receiving other anti-cancer agents are not eligible [except patients receiving hydroxyurea, which may be continued until 24 hours prior to start of protocol therapy].

4.2.2.4 CYP3A4 Agents: Patients who are currently receiving drugs that are strong inhibitors and/or inducers of CYP3A4 or sensitive CYP3A4 substrates and CYP3A4 substrates with a narrow therapeutic range are not eligible. Strong inducers or inhibitors of CYP3A4 are prohibited from 14 days prior to enrollment to the end of the study. See [Appendix III](#) for a list of agents.

4.2.2.5 Anti-GVHD agents post-transplant: Patients who are receiving cyclosporine, tacrolimus or other agents to prevent graft-versus-host disease post bone marrow transplant.

4.2.3 Patients must be able to swallow intact capsules or liquid. Patients that are unable to swallow oral medications may receive palbociclib oral solution through an NG tube. G tube administration is not allowed.

4.2.4 Infection: Patients who have an uncontrolled infection defined as below:

- Positive bacterial blood culture within 48 hours of study enrollment;
- Fever above 38.2°C within 48 hours of study enrollment with clinical signs of infection. Fever that is determined to be due to tumor burden is allowed if patients have documented negative blood cultures for at least 48 hours prior to enrollment and no concurrent signs or symptoms of active infection or hemodynamic instability.
- A positive fungal culture within 30 days of study enrollment or active therapy for presumed invasive fungal infection.

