8.0 EVALUATIONS/MATERIAL AND DATA TO BE ACCESSIONED

8.1 Required Clinical, Laboratory and Disease Evaluation

All clinical and laboratory studies to determine eligibility must be performed within 7 days prior to enrollment unless otherwise indicated. Laboratory values used to assess eligibility (see [Section 4.0](#)) must be no older than seven (7) days at the start of therapy. Laboratory tests need **not** be repeated if therapy starts **within** seven (7) days of obtaining labs to assess eligibility. If a post-enrollment lab value is outside the limits of eligibility, or laboratory values are older than 7 days, then the following laboratory evaluations must be re-checked within 48 hours prior to initiating therapy: bilirubin, ALT (SGPT) and serum creatinine. If the recheck is outside the limits of eligibility, the patient may not receive protocol therapy and will be considered off protocol therapy. Imaging studies, bone marrow aspirate and/or biopsy, must be obtained within 14 days prior to start of protocol therapy (repeat the tumor imaging if necessary).

STUDIES TO BE OBTAINED	Pre-Study	During Cycle 1	End of Protocol Therapy- Day 32[^]
History	X	Weekly	
Physical exam with vital signs	X	Weekly	X
Height, weight, BSA	X		X
Performance status	X		X
Pregnancy test ¹	X		
CBC, differential, platelets	X	Twice Weekly (every 3 to 4 days) ³	X
CSF cell count & cytospin	X*	With each IT	
Pharmacokinetics ²	X	X	
Urinalysis	X		
Electrolytes including Ca ⁺⁺	X	Weekly	X
Creatinine, ALT, bilirubin	X	Weekly	X
Direct Bilirubin	X ¹²		
Albumin	X		
ECHO or gated radionuclide study	X		X
12-lead EKG	X		X
Chest x-ray	X		
Patient Diary ¹¹		Weekly	X
ADDITIONAL STUDIES: ALL ONLY			
Bone marrow aspirate for morphology and MRD	X		X ⁴
Absolute Blast Count (ABC)		Day 4 ⁵	
Correlative biology studies ⁶	X	Day 4	X
ADDITIONAL STUDIES: LL ONLY			
Chest ⁷ and neck CT	X		X ^{7,8}
Abdomen/Pelvis CT or MRI	X		X ⁸
Chest x-ray	X		
PET scan (recommended)	X		X
Bone scan ⁹	X ⁹		X ⁹
Bilateral bone marrow aspirates and biopsies for morphology	X		Only if positive at diagnosis ¹⁰

- [^] Abnormal laboratory tests must be re-checked by Day 42 since some toxicities require resolutions to \leq Grade 2 or baseline by Day 42 (see DLT criteria).
- * May be done with the Day 1 lumbar puncture with IT therapy.

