8.3.2 Sampling Schedule (See Appendix II)

One bone marrow or blood sample (10-15mL) for each time point will be collected to assess for the studies outlined below. Peripheral blood also can be

substituted or used to augment bone marrow samples if the absolute blast count is >1000/ μ L: 10 mL per samples (<10 kg) or 15 mL (\geq 10 kg).

	Pre-study Marrow	Day 4 Blood	Day 32* Marrow
Targeted DNA sequencing to identify somatic mutations in both T-ALL and B-ALL samples	X		
CDKN2A deletions (using FISH)	X		
RB1 expression and RB1 phosphorylation status (Immunoblotting)	X	X**	X
p27 ^{Kip1} expression (Immunoblotting)	X	X**	X
Cyclin D3 and CDK4/6 protein expression (Immunoblotting)	X	X**	X
Cell cycle analysis (response to Palbociclib)	X	X**	X
Peripheral blood absolute blast count	X	X**	

* End of therapy analyses in patients with persistent disease. End of therapy analyses must be obtained on Day 32 \pm 2 days.

** Peripheral blood samples should be collected PRIOR to administration of Day 4 chemotherapy, if absolute blast count is >1000/mm³

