³The effect of grapefruit juice (strong vs moderate CYP3A4 inhibition) varies widely among brands and is concentration-, dose-, and preparation-dependent.

⁴Narrow therapeutic range substrates

⁵Sensitive substrates (drugs that demonstrate an increase in AUC of ≥ 5 -fold with strong inhibitors)

**APPENDIX IV: ADDITIONAL INFORMATION FOR CORRELATIVE BIOLOGY STUDIES:
DETERMINING THE BIOLOGICAL ACTIVITY OF PALBOCICLIB**

Overview: Assays will be performed prior to and following palbociclib administration as summarized in Table 1 to determine the efficiency of cell cycle inhibition.

Table 1. Correlative Biology Studies

	Pre-study	Day 4	Day 32*
Targeted DNA sequencing to identify somatic mutations in both T-ALL and B-ALL samples	X		
CDKN2A deletions (using FISH)	X		
RB1 expression and RB1 phosphorylation status (Immunoblotting)	X	X**	X
p27 ^{Kip1} expression (Immunoblotting)	X	X**	X
Cyclin D3 and CDK4/6 protein expression (Immunoblotting)	X	X**	X
Cell cycle analysis (response to Palbociclib)	X	X**	X
Peripheral blood absolute blast count	X	X**	

* End of therapy analyses in patients with persistent disease. End of therapy analyses must be obtained on Day 32 ± 2 days.

** Submit peripheral blood samples if absolute blast count is >1000/mm³

Experimental Design:

Bone marrow and peripheral blood samples (5 mL) will be collected at the time points summarized in Table 1. The pre-study and Day 32 time points coincide with times when bone marrow aspirates are performed as a part of routine clinical care so that extra procedures will not be done exclusively for research tests. Peripheral blood also can be substituted or used to augment bone marrow samples if the absolute blast count is >1000/mm³: 10 mL per samples (<10 kg) or 15 mL (≥ 10 kg).

Lymphoblasts will be isolated from bone marrow within 4 hours of collection using Ficoll-Paque Plus (Amersham Biosciences, Brown Deer, WI) at participating COG Phase 1 centers to avoid potential artifacts associated with prolonged sample storage or shipping. Blasts will then be frozen and batch shipped on dry ice to the [name]/[name] labs for DNA and protein purification. One third of the cells will be used for DNA sequencing and two thirds of cells per sample will be used for protein expression. Freshly harvested blasts will be collected and fixed prior to shipment for the proposed cell cycle analyses (see Appendix II for details regarding samples processing).

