- 3) Dual-Colour FISH for detection of *CDKN2A* deletions.** *CDKN2A* deletions will be detected using fluorescence in situ hybridization (FISH) analysis as it is currently done in solid tumors. Dual-color FISH will be performed using a commercially available Spectrum Orange-labelled locus specific p16 (9p21) probe and Spectrum Green-labelled chromosome 9 centromeric probe [Vysis LSI p16 (9p21) SpectrumOrange/CEP9 SpectrumGreen Probe; Abbott Laboratories, Des Plaines, Illinois, USA] as previously described.³⁹ ALL cells will be cytospun on slides for FISH analysis. After washing in 2X standard saline citrate for 5 min, sections will be digested with pepsin (37 500 U in 0.1 N HCl) (Sigma, St Louis, Missouri, USA) at 37°C for 10–25 min. Slides will be co-denatured with the probes, allowed to hybridize and washed according to the manufacturer's protocol. Slides will be analyzed, blinded from the clinical data, using a Zeiss microscope (Axioplan 2, Jena, Germany) equipped with the appropriate filters. A minimum of 100 non-overlapped intact (uniform DAPI staining with intact nuclear contours) interphase nuclei of consecutive cells in at least two different areas of the section will be scored.
- 4) Cell Cycle Analysis.** We will use standard flow cytometry protocols to combine surface staining for T-ALL markers (CD1a, CD3, CD4, CD8) and intracellular staining for the cell cycle (and apoptosis) markers Ki67 and DAPI. For intracellular Ki67 and DAPI staining in T-ALL cells, following staining of surface antigens, bone marrow/peripheral T-ALL cells will be fixed with 4% paraformaldehyde and permeabilized with 0.1% saponin prior to addition of anti-Ki67 (BD Biosciences) and 2 µg/mL DAPI. A similar procedure will be followed for B-ALL.

As an early measure of response to single agent palbociclib, the absolute peripheral blast count will be measured at baseline and after 72 hours of drug exposure.

For pre- and post-treatment measurements of absolute peripheral blast count protein expression, pairwise comparisons will be made using Fisher's exact test and paired t-test or an equivalent nonparametric tests as appropriate. Baseline expression of cell cycle proteins and the presence of somatic mutations and *CDKN2A* deletions will be correlated with treatment response. These analyses will be descriptive and exploratory in nature.

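### The 72-hour blast-count measure has no fixed baseline time, so a fall before the first palbociclib dose, such as one from permitted cytoreduction, can be credited to palbociclib

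*Combined protocol and SAP*

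**What the plan says.** **The measure.** Appendix IV states: "As an early measure of response to single agent palbociclib, the absolute peripheral blast count will be measured at baseline and after 72 hours" (that is, on the drug). It then plans paired comparisons of pre- and post-treatment values and calls the analyses descriptive and exploratory.

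**The two time points.** The tables in Section 8.3.2 and Appendix IV have a row for "Peripheral blood absolute blast count", marked at pre-study and Day 4. Appendix IV adds: "Assays will be performed prior to and following palbociclib administration as summarized in Table 1". The required-evaluations table in Section 8.1 lists the absolute blast count on Day 4 only, although its pre-study CBC with differential could supply a baseline. Footnote 5 of that section places the Day 4 count before chemotherapy. No corresponding note ties the baseline to a day or hour.

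**What may happen before Day 1.** Section 4.2.2.1 says that prednisone or methylprednisolone, for at most 120 hours, "may be administered for cytoreduction up to 24 hours prior to the start of protocol therapy". Section 4.2.2.3 bars other anti-cancer agents "except patients receiving hydroxyurea, which may be continued until 24 hours prior to start of protocol therapy", and neither it nor Section 4.1.5.1 limits how long hydroxyurea may be given. Section 4.1.5.1 also requires no waiting period after standard maintenance, which may include a corticosteroid.

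**Age of laboratory values.** Section 8.1 says that values used for eligibility "must be no older than seven (7) days at the start of therapy". If they are older, the listed tests "must be re-checked within 48 hours prior to initiating therapy: bilirubin, ALT (SGPT) and serum creatinine"; a blood count is not among them. Under Section 3.9 the projected start "must be no later than five (5) calendar days after the date of study enrollment".

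**The concern.** A before-and-after change can be read as a drug effect only if the before value is taken just before the drug. The plan protects the Day 4 end of the interval and leaves the starting end open. Steroids and hydroxyurea are given before Day 1 precisely to lower the leukemic cell count. If the baseline count is drawn before they are, the paired comparison includes whatever fall they cause, and no planned analysis excludes or adjusts for it.

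What is at stake is secondary aim 1.2.2, on biologic activity. Doxorubicin, prednisone and vincristine all begin on Day 4, so Days 1 to 3 are the only part of the regimen that comes close to palbociclib alone. A Day 1 count that was not collected cannot be recovered at analysis.

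**Working it through.** The plan gives no sample size, effect size or error rate for this measure, so there is no design figure to reproduce. The check is on timing.

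**Inputs.** Steroid course of at most 120 h, ending 24 h before start (Section 4.2.2.1). Eligibility laboratory values at most 7 days old at start (Section 8.1). Eligibility studies within 7 days before enrollment (Section 8.1), and start within 5 days after it (Section 3.9). Second count on Day 4 (Section 8.1, footnote 5). Protocol therapy is first taken to start with palbociclib on Day 1.

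**Step 1: exposure time.** Day 1 to Day 4 is 3 × 24 = 72 h, which agrees with Appendix IV.

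**Step 2: earliest start of a full steroid course.** 120 + 24 = 144 h before Day 1.

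**Step 3: share of the interval that precedes the first dose.** With a baseline count A hours before Day 1, the share is A / (A + 72).

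| Baseline count | A (h) | Interval to Day 4 (h) | Share before first dose | Margin before a full steroid course (A − 144) |
|---|---|---|---|---|
| Day 1, pre-dose | 0 | 72 | 0% | count follows the course |
| 7 days old | 168 | 240 | 70% | 24 h |
| 12 days old (inference) | 288 | 360 | 80% | 144 h |

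The 12-day row adds 7 days before enrollment to 5 days from enrollment to start, and relies on the short re-check list. No section states it as a permitted age for this count.

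**Step 4: sensitivity to the start of therapy.** Section 4.1.5.1 counts intrathecal treatment given up to 72 h before systemic chemotherapy as protocol therapy. Suppose that moves the start to 72 h before Day 1. A full steroid course then ends at 72 + 24 = 96 h and begins at 96 + 120 = 216 h before Day 1. A 168 h count falls 216 − 168 = 48 h into the course, with 168 − 96 = 72 h of steroid still to come. If the 7-day laboratory limit also runs from the earlier start, the count can be 168 + 72 = 240 h before Day 1, and the margin is again 240 − 216 = 24 h. On either reading, steroid treatment can follow the baseline count.

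**Step 5: can the size be estimated?** Not from the documents. As an assumption only, let palbociclib have no effect, and let a share f of patients have their count cut by a fraction r after baseline. The apparent geometric-mean change is (1 − r)^f − 1. With f = 0.25 and r = 0.3 this is −9%; with f = 0.5 and r = 0.5, −29%; with f = 1 and r = 0.8, −80%. The documents give no basis for choosing among these. They show the mechanism and are not an estimate.

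**The case against.** The strongest reply is that the plan already implies a pre-drug baseline. Appendix IV speaks of assays before and after palbociclib, and the Appendix IX form labels its first sample as preceding the Day 1 dose, with date and time fields. This narrows the gap without closing it. The label belongs to the marrow or blood sample and sets a latest time but no earliest one. The form has a field for the Day 4 count and none for a baseline count.

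A second reply is that the seven-day laboratory rule covers the count. That is arguable, since the rule governs values used for eligibility and Section 4.1.6 sets no blood-count threshold. Even where it applies, it does not place the count after cytoreduction.

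A third is that the analysis is exploratory, belongs to optional correlative work and carries no decision rule. That stands, and it limits the weight of the point.

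A reader might also infer several stronger things that the documents do not support:

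- That 70% or 80% of an observed fall would be spurious. These are shares of elapsed time in particular timing cases, not of effect.
- That the error always favours palbociclib. In patients with growing disease and no cytoreduction, an old baseline would understate a fall.
- That intrathecal chemotherapy falls inside the 72 hours for every patient. Sections 3.9 and 4.1.5.1 allow the Day 1 intrathecal dose to be given earlier, at the diagnostic lumbar puncture, so this is true of some patients and perhaps not of others.

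**Conclusion.** The point holds as a minor one. The plan labels the change from baseline to 72 hours as response to palbociclib alone, but it neither fixes the baseline close to the first dose nor places it after permitted cytoreduction. The 70% figure assumes that therapy starts on Day 1 and that the count is seven days old; the 80% figure is an inference. The missing timing rule is clear from the text. The size of the resulting bias, and its net direction across patients, is unknown because the documents give neither the frequency of cytoreduction nor its effect.

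It would be wrong to conclude that the dose finding is affected. The measure plays no part in DLT assessment, the MTD/RP2D decision or the response criteria of Section 12.

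**What to change.** 1. Define the baseline for this measure as the absolute blast count on Day 1 before the first palbociclib dose, taken at the pre-dose pharmacokinetic draw already required by Section 8.2.2 and Appendix VIII. Add a field for it, with date and time, to the Appendix IX form.
2. As a descriptive sensitivity summary, report the Day 1 to Day 4 change overall and separately for patients with and without each of: recent cytoreduction, recent steroid-containing maintenance, and intrathecal chemotherapy inside the interval. Use recorded dates and a look-back window that the sponsor prespecifies; the documents supply none. The case report form packet is separate (Section 14.1) and was not available, so date fields need adding only if it lacks them.

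The cost is one extra count at an existing draw, one form field and a few lines of analysis text. No treatment or eligibility rule changes. The limits should be stated: the subgroups will be small, since Section 11.1 foresees about six patients per dose level and up to six in the expansion, and a Day 1 baseline does not fully remove steroid or hydroxyurea effects that carry over past Day 1.

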APPENDIX V-A: Palbociclib Capsule Dosing Nomogram

Drug doses should be adjusted based on the BSA calculated from height and weight measured within 7 days prior to the beginning of each cycle.

Palbociclib is available as 75 mg and 100 mg capsules. Patients receiving doses ≥ 75 mg/day may take either the capsule or liquid formulation. Patients receiving < 75 mg/day of palbociclib must receive the liquid formulation (See [Appendix V-B](#) for dosing preparation of palbociclib liquid formulation.)

**Palbociclib Dose Assignment: 50 mg/m²
(Dose Level 1)**

BSA (m ²)	Total Daily Dose (mg/day)	Dose Reduction for Toxicity (mg/day)
< 1.37	Use liquid formulation (see Appendix V-B)	Reduce dose by 30%. Use liquid formulation (see Appendix V-B)
1.37-1.74	75	Reduce dose by 30%. Use liquid formulation (see Appendix V-B)
≥ 1.75	100	75

**Palbociclib Dose Assignment: 35 mg/m²
(Dose Level -1)**

BSA (m ²)	Total Daily Dose (mg/day)	Dose Reduction for Toxicity (mg/day)
<1.95	Use liquid formulation (see Appendix V-B)	off protocol therapy
≥ 1.95	75	off protocol therapy

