5.0 TREATMENT PROGRAM

5.1 Overview of Treatment Plan

DRUG	ROUTE	DOSAGE	DAYS
Palbociclib IND# 141416	PO (or via NG- tube)	DL1: 50 mg/m ² (max 100 mg/day) DL-1: 35 mg/m ² (max 75 mg/day)	Once daily on Days 1-21
Intrathecal Cytarabine (IT ARAC): All patients on Day 1 (before CNS status is known)[@]	IT	Age (yrs) Dose 1-1.99 30 mg 2-2.99 50 mg ≥3 70 mg	1 [@]
Intrathecal Methotrexate (IT MTX): CNS1 and 2	IT	Age (yrs) Dose 1-1.99 8 mg 2-2.99 10 mg 3-8.99 12 mg ≥9 15 mg	18,32
Intrathecal Triple Therapy (ITT)[@]: Methotrexate (MTX)/ Hydrocortisone (HC)/Cytarabine (ARAC) if CNS3	IT	Age (yrs) Dose 1-1.99 MTX:8mg, HC: 8mg, ARAC: 16mg 2-2.99 MTX: 10mg HC: 10 mg ARAC: 20 mg 3-8.99 MTX: 12 mg HC: 12 mg ARAC: 24 mg ≥9 MTX: 15 mg HC: 15 mg ARAC: 30 mg	1 [@] , 4, 11, 18, 25
Doxorubicin (DOXO)	slow IV push or infusion over 1-15 min	60 mg/m ² /dose	4
PredniSO(LO)NE (PRED)*	PO	40 mg/m ² /day divided BID or TID	4-31
VinCRiStine (VCR)	IV push or mini-bag per institutional policy	1.5 mg/m ² /dose (MAX dose 2 mg)	4, 11, 18, 25
Pegaspargase (PEG-ASP)[#]	IV over 1-2 hours	2500 International units/m ² /dose	5, 18

* IV methylprednisolone may be given at 80 % of the oral predniSONE or predniSOLONE dose
If allergic to PEGaspargase then see [Section 6.2.1](#) for Asparaginase *Erwinia Chrysanthemii* dosing.

[@] Patients with known CNS3 disease at the time of study enrollment may receive triple intrathecal chemotherapy on Day 1 **as a substitute for** intrathecal cytarabine, at the discretion of the treating investigator. Patients are **NOT** to receive both intrathecal triples and intrathecal cytarabine on Day 1, regardless of CNS status.

A cycle of therapy is considered to be 32 days. Please see Therapy Delivery Maps (TDMs) in [Appendix VI](#) (patients with ALL) and [Appendix VII](#) (Patients with LL).

It is recommended that drugs be administered in the order listed below.

Drug doses should be adjusted based on the BSA calculated from height and weight obtained within one week prior to the beginning of protocol therapy. For patients able to swallow capsule, please refer to the dosing nomogram in [Appendix V-A](#). Patients unable to swallow capsules should use the oral solution, please refer to [Appendix V-B](#).

Palbociclib: PO (or via NG- tube)

Days: Once daily on Days 1-21

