5.2 Dosing Schema

5.2.1 Inter-Patient Dosing Schema

Dose Level	Palbociclib (mg/m ²)	Palbociclib max dose (mg/day)
-1	35	75
1*	50	100

If the MTD has been exceeded at the first dose level, then the subsequent cohort of patients will be treated at a dose of 35 mg/m² (Dose Level -1). If Dose Level -1 is not well tolerated, further de-escalation will not occur. The study will be closed to accrual.

See [Appendix V-A](#) and [Appendix V-B](#) for palbociclib capsule and liquid formulation dosing.

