6.1 Dose Modifications for Non-Hematological Toxicity Attributable to Palbociclib

- 6.1.1 If a patient experiences non-hematological dose-limiting toxicity as defined in [Section 5.4.1](#), palbociclib will be held until the toxicity is \leq Grade 1 or as otherwise indicated below (see [Section 6.2](#) for dose modifications for other backbone chemotherapy agents). When the toxicity resolves to meet eligibility parameters or baseline within 14 days of drug discontinuation, the patient may resume treatment at the next lower dose level. For patients enrolled at Dose Level -1, palbociclib should be discontinued but the backbone chemotherapy can be continued if this is not contributing to the toxicity. Doses reduced for toxicity will not be re-escalated, even if there is minimal or no toxicity with the reduced dose. Missed doses will not be made up.
- 6.1.2 If toxicity does not resolve to meet eligibility or baseline parameters within 14 days of drug discontinuation, the patient must be removed from protocol therapy.
- 6.1.3 If a dose-limiting toxicity recurs in a patient who has resumed treatment at the reduced dose level, the patient must be removed from protocol therapy.

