APPENDIX V-B: PALBOCICLIB DOSING PREPARATION (LIQUID FORMULATION)

Drug doses should be adjusted based on the BSA calculated from height and weight measured within 7 days prior to the beginning of the cycle.

Patients receiving doses ≥ 75 mg/day may take either the capsule or liquid formulation. (See [Appendix V-A](#) for dosing nomogram for palbociclib capsule formulation).

Patients receiving < 75 mg/day of palbociclib must receive the liquid formulation.

Patients receiving the liquid formulation who experience dose-limiting toxicity should have their dose reduced by 30%, so that patients receive 70% of the original prescribed dose.

The concentration of palbociclib liquid formulation is 25 mg/mL.

Calculated doses < 18.75 mg should be prepared in oral syringes ≤ 1 mL with dosing volumes of palbociclib liquid formulation rounded to the nearest 0.1 mL (2.5 mg). Calculated doses > 18.75 mg should be prepared in 5 mL oral syringes with dosing volumes of palbociclib liquid formulation rounded to the nearest 0.2 mL (5 mg). It is recommended that oral dosing syringes should be only filled up to 75% of the maximum volume.

To calculate dosing volumes for each patient based on BSA, the following formula should be used:

$$\text{Dosing Volume (mL)} = \frac{\text{Prescribed Dose (mg/m}^2\text{)} \times \text{BSA (m}^2\text{)}}{25 \text{ (mg/mL)}}$$

Round dosing volumes according to the above rules.

Examples:

- Patient BSA 0.33 m^2 , Dose Level 1 (50 mg/m^2) \rightarrow Calculated Dose = 16.5 mg PO daily
 Calculated Volume (mL) = $(50 \text{ mg/m}^2 \times 0.33 \text{ m}^2) / (25 \text{ mg/mL}) = 0.66 \text{ mL}$
 Final Dosing Volume (mL) = 0.7 mL (rounded to nearest 0.1 mL for doses ≤ 18.75 mg)
 Final Dose to be administered = $0.7 \text{ mL} \times 25 \text{ mg/mL} = 17.5 \text{ mg}$
- Patient BSA 1.66 m^2 , Dose Level -1 (35 mg/m^2) \rightarrow Calculated Dose = 58.1 mg PO daily
 Calculated Volume (mL) = $(35 \text{ mg/m}^2 \times 1.66 \text{ m}^2) / (25 \text{ mg/mL}) = 2.324 \text{ mL}$
 Final Dosing Volume (mL) = 2.4 mL (rounded to the nearest 0.2 mL for dose > 18.75 mg)
 Final Dose to be administered = $2.4 \text{ mL} \times 25 \text{ mg/mL} = 60 \text{ mg}$

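### For Dose Level 1 patients with BSA 1.75–1.94 m², Appendix V-A's reduced palbociclib dose of 75 mg is higher than the Dose Level -1 dose that Section 6.1.1 calls for

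*Combined protocol and SAP*

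**What the plan says.** Section 6.1.1 covers a patient who has had a non-hematological DLT. Once the toxicity has resolved in time, "the patient may resume treatment at the next lower dose level". The level below Dose Level 1 is set in Section 5.2.1, where the next cohort would be "treated at a dose of 35 mg/m² (Dose Level -1)", and the table in Section 5.1 adds the cap: "DL-1: 35 mg/m ² (max 75 mg/day)".

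Appendix V-A turns these levels into daily doses by BSA.

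- **Dose Level 1 table, column for reduction after toxicity.** For BSA below 1.75 the entry is "Reduce dose by 30%. Use liquid formulation". For BSA 1.75 and above, the starting dose is 100 mg and the reduced dose is 75 mg.
- **Dose Level -1 table.** The lower row reads "<1.95 Use liquid formulation" and the upper row reads "≥ 1.95 75 off protocol therapy".
- **Formulation limit.** "Patients receiving < 75 mg/day of palbociclib must receive the liquid formulation".

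Appendix V-B has its own reduction rule. Patients on the liquid who have a DLT "should have their dose reduced by 30%, so that patients receive 70% of the original prescribed dose". It also rounds liquid doses above 18.75 mg to the nearest 0.2 mL, which is 5 mg at 25 mg/mL.

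**The concern.** A Dose Level 1 patient with BSA between 1.75 and 1.94 who has just had a DLT gets two answers from the protocol. Section 6.1.1, read with the Dose Level -1 table, gives liquid at 35 mg/m². The Dose Level 1 table gives 75 mg. Nothing in the protocol says which governs, and Section 6.1.1 does not refer to Appendix V-A.

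The order of the doses is also the wrong way round. In this band, a patient moved down after a DLT receives more palbociclib than a patient of the same size newly assigned to Dose Level -1. Under Section 6.1.3, a DLT that recurs at the reduced dose removes the patient from protocol therapy. The dose in this row can therefore bear on whether an individual stays on treatment.

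**Working it through.** **Inputs.** Dose Level 1 is 50 mg/m² with a maximum of 100 mg; Dose Level -1 is 35 mg/m² with a maximum of 75 mg (Sections 5.1 and 5.2.1). Capsule bands and reduced doses come from Appendix V-A, and liquid rounding to 5 mg from Appendix V-B.

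**1. Can the 75 mg be reproduced?** The next lower level gives min(75, 35 × BSA), delivered as in the Dose Level -1 table: liquid rounded to 5 mg below BSA 1.95, and 75 mg from 1.95. This yields 75 mg for BSA 1.95 and above, but not for 1.75–1.94. A 30% cut from 100 mg gives 0.70 × 100 = 70 mg, which is not 75 mg at any BSA.

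**2. Size of the gap.** Excess = 75 / (Dose Level -1 dose) − 1.

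| BSA (m²) | 75 mg as mg/m² | 35 × BSA (mg) | Excess over calculated | Dose Level -1 dose as given (mg) | Excess over dose as given |
|---|---|---|---|---|---|
| 1.75 | 42.9 | 61.25 | 22.4% | 60 | 25.0% |
| 1.80 | 41.7 | 63.0 | 19.0% | 65 | 15.4% |
| 1.85 | 40.5 | 64.75 | 15.8% | 65 | 15.4% |
| 1.90 | 39.5 | 66.5 | 12.8% | 65 | 15.4% |
| 1.94 | 38.7 | 67.9 | 10.5% | 70 | 7.1% |
| 1.95 | 38.5 | 68.25 | 9.9% | 75 (capsule row) | 0% |

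At BSA 1.80, for example, a patient newly assigned to Dose Level -1 takes 65 mg, while a patient moved down after a DLT takes 75 mg.

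**3. Is this only the nomogram's usual rounding?** The upward rounding in the assigned-dose columns is largest at the lower edge of each capsule band:

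- BSA 1.37: 75 / (50 × 1.37) = 75/68.5 = 1.095
- BSA 1.75: 100/87.5 = 1.143
- BSA 1.95: 75/68.25 = 1.099

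The largest is 14.3%. The reduced dose exceeds 35 mg/m² by more than that when BSA is below 75 / (35 × 1.143) = 1.875. Above 1.875 the excess is within the rounding that the nomogram accepts elsewhere, although the two tables still give different doses.

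**4. Comparison with the 30% rule.** Since 0.70 × 50 = 35, a 30% cut from the calculated Dose Level 1 dose is the same as moving to Dose Level -1, until the 100 mg cap applies at BSA 2.00. The step from 100 to 75 mg is a 25% cut. At BSA 1.75, before rounding, a liquid patient goes from 87.5 mg to 61.25 mg and a capsule patient from 100 mg to 75 mg.

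**5. The step at BSA 1.75.** At BSA 1.74 the reduced dose before rounding is 52.5 mg if the 30% is taken from the 75 mg capsule dose, or 60.9 mg if it is taken from 50 mg/m². At BSA 1.75 it is 75 mg, which is also the full Dose Level 1 capsule dose at BSA 1.74.

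**The case against.** **Much of the 22% comes from the starting dose.** At BSA 1.75 the 100 mg capsule is already 14.3% above 50 mg/m². The reduction step adds only 75/70 = 1.071, and 1.143 × 1.071 = 1.224. This is correct and explains where the excess comes from. It does not remove the conflict, because Section 6.1.1 sends the patient to a dose level, and at this BSA the protocol delivers that level as liquid without capsule banding.

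**75 mg is the only capsule step down.** Only 75 mg and 100 mg capsules are listed, so 75 mg avoids a change of formulation. But the row for BSA 1.37–1.74 already moves capsule patients to liquid on reduction, so the appendix does not treat keeping the capsule as a requirement.

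**Sites are told where to look.** Sections 5.1 and 5.2.1 refer capsule patients to Appendix V-A, which has an explicit column for the reduced dose. A site may well follow it. That makes the dose given predictable, but it would then be the one that departs from Section 6.1.1.

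**The neighboring row is not exact either.** If the 30% is taken from the 75 mg capsule, the result is 52.5 mg against 47.95 to 60.9 mg at 35 mg/m², between 9.5% above and 13.8% below. This stands. That row can, however, be read as 70% of the calculated dose, which agrees with Section 6.1.1; the fixed 75 mg entry allows no such reading.

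**Conclusion.** The inconsistency is real but narrow. For Dose Level 1 patients with BSA 1.75–1.94, Appendix V-A's reduced dose is 22% (at 1.75) to 10% (at 1.94) above the calculated dose under Section 6.1.1. It is clearest below about BSA 1.875. It matters only for a patient who would take the capsule, has a non-hematological DLT, and recovers in time to restart within the 21 palbociclib days. The protocol gives no BSA distribution, so the expected number cannot be calculated. It will be few in a study of at most 36.

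Three stronger readings are tempting, and the documents do not support them.

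- A reader might infer that the whole row from BSA 1.75 is wrong. From 1.95 upward, 75 mg is both the dose in the Dose Level -1 table and that level's cap.
- A reader might infer that the 25% cut breaches Appendix V-B. That rule is limited to patients on the liquid, so for capsule patients 25% versus 30% is a secondary inconsistency between formulations.
- A reader might infer that the MTD decision is affected. The reduction follows a DLT that already counts for that patient, so the rules in Sections 11.2.2 and 11.3 and the sample size are unchanged.

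The conclusion assumes that the next lower dose level in Section 6.1.1 means Dose Level -1 as set out in Section 5.2.1 and delivered as in Appendix V-A.

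**What to change.** Split the reduction entry of the Dose Level 1 table in Appendix V-A at BSA 1.95:

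- BSA 1.75–1.94: reduce to liquid at 35 mg/m², about 60–70 mg after rounding to 5 mg.
- BSA 1.95 and above: reduce to 75 mg, as now.

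If the sponsor's clinical team intends 75 mg for the whole row, Section 6.1.1 should state that exception and refer to the table. The choice of dose is theirs. The same edit could say whether the 30% in the rows below BSA 1.75 is taken from the capsule dose or from the calculated dose.

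The cost is a table edit and, for the few patients affected, a switch from capsule to liquid. No change to the statistical section is needed.
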